6.4 Missing data

The number of patients with non-missing observations will be reported for each outcome.

Missing data may occur due to drop-outs or deaths. The former will lead the absence of all outcome information as outcomes are only assessed once. Since the follow-up is very short we do not expect a lot of drop-outs and it is unlikely that these patients did have a readmission or died. Therefore, we will assume that drop-outs did not have a readmission and did not die. For survival analyses they will be censored at one day. For count outcomes they will be assumed to have no observed event and an offset of one day. For patient satisfaction multiple imputations will be used (section 6.4.1). If the amount of drop-outs is larger than 5%, we will do a sensitivity analysis in which the primary outcome (unplanned readmission or death) will be multiply imputed as a binary variable (section 6.4.1).

Death will not lead to missing data for the primary outcome, 30-day deaths and time to primary outcome. For 30-day unplanned readmission, death is a competing event and the cumulative incidence at 30 days will be used (section 6.3.1.2). Count outcomes will be handled by including the observation time as offset in the Poisson regression. For patient satisfaction multiple imputations will be used (section 6.4.1). In a sensitivity analysis, the worst possible outcome will be assigned to deaths (i.e. a negative respond to all question of the CTM-3).

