2.3 Sample size

Because we will target patients at higher risk of readmission, we hypothesize that the intervention could reduce the relative risk of readmission by 25%, i.e. more than the 18% reduction found in a recent meta-analysis where patients were mostly not at high risk for readmission. Based on previous findings, the expected 30-day readmission and death rate for patients at intermediate or high risk according to the simplified HOSPITAL score is around 27%. Allowing for 10% loss to follow-up, we determine that we will need 1,380 patients for the study to have 80% power, i.e. 690 in each arm.

The intervention phase (randomized controlled trial) will be restricted to the eligible patients who are at intermediate to high risk of 30-day readmission according to the simplified HOSPITAL score, i.e. $\geq 4/13$ points. We estimate to have around 18,000 patients discharged during the 20-month study period, 30% of which (5,400) will be at higher-risk for a 30-day readmission or death. This should be enough to reach the targeted sample size within the study time frame.

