6.3 Analysis methods

6.3.1 Primary analysis

The primary analysis will be based on the FAS. Missing data will be handled according to section 6.4.

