6.3.2 Secondary analyses

All outcomes will also be analyzed in the PPS. Only patients without missing value for the respective outcome will be considered (complete cases).

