6.3.3 Sensitivity analyses

The following sensitivity analysis will be included for all outcomes:

- 1) Without early readmissions. The primary endpoint will be re-analyzed excluding the patients with unplanned readmissions up to the day after index discharge (i.e. unplanned_1_in - disch_date_index <=1)
- 2) No stratification: All outcomes will be analyzed in crude analyses not adjusting for stratification factors. Binary outcomes will be compared by chis-squared test, continuous outcomes by Student's t-test or the Wilcoxon-Mann-Whitney test, count outcomes using an exact Poisson-test and time-to-event outcomes by a log-rank test. Effects will be presented as non-stratified risk difference, mean difference or Mann-Whitney statistic (i.e. the probability that a random patient from the intervention group will have a higher value than a random patient from the control group), incidence rate ratio, and restricted mean survival time difference, respectively, with 95% CI.
- 3) Primary endpoint based on survival methods. The risk of readmission or death at 30 days for both groups and the risk difference between groups will be calculated with 95% CI and p-values from a z-test using a) a flexible parametric survival model for time to unplanned readmission or death with the group and stratification factors as covariates and b) from the Kaplan-Meier-estimator for time to unplanned readmission or death not using the stratification. CIs for the risk differences and the z-test will be calculated using delta method standard errors and a normal approximation.
- 4) Non-parametric unplanned readmissions: The risk of unplanned readmission at 30 days in the presence of the competing risk of death will be calculated for each group using the non-parametric cumulative incidence function estimator with 95% CI according to Choudhury et al⁸. Stratification will be ignored.

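### The primary analysis counts every drop-out as event-free, which shrinks the risk difference and biases it if loss differs by arm

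*SAP*

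**What the plan says.** Section 6.3.1 bases the primary analysis on all randomized patients and adds: "Missing data will be handled according to section 6.4". Section 6.4 says of drop-outs: "The former will lead the absence of all outcome information as outcomes are only assessed once". It expects few of them, calls an event in them unlikely, and concludes: "Therefore, we will assume that drop-outs did not have a readmission and did not die".

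Section 2.3 expects a 30-day event rate of about 27% and a 25% relative reduction, and sizes the trial as follows: "Allowing for 10% loss to follow-up, we determine that we will need 1,380 patients for the study to have 80% power".

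Three other analyses bear on the point:

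- Section 6.4: "If the amount of drop-outs is larger than 5%, we will do a sensitivity analysis", in which the primary outcome is multiply imputed.
- Section 6.3.3, item 3, under the label "Primary endpoint based on survival methods", re-estimates the 30-day risk difference with a flexible parametric model and by Kaplan-Meier. Section 6.4 censors drop-outs at one day for survival analyses.
- Section 6.3.2 repeats all outcomes in the per-protocol set on complete cases.

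**The concern.** A patient with no outcome information is entered in the primary comparison as an observed non-event. Short follow-up may explain why few patients drop out. It does not explain why those who do should have no events, in a population selected for a high event rate over that same window. Section 2.3 inflates the sample as if lost patients contribute nothing, whereas section 6.4 analyses them as known successes.

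Two consequences follow if drop-outs carry real risk. Equal loss pulls the risk difference towards zero in proportion to the loss. Unequal loss makes the arm that loses more patients look better, even with no treatment effect. Unequal loss is plausible because contact differs by design: Table 10 in section 7 notes that only the intervention group has follow-up calls. The SAP gives no basis for predicting which arm would lose more. The 5% trigger is not defined by arm, so it cannot detect an imbalance.

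**Working it through.** **Inputs.** From section 2.3: control risk 0.27; intervention risk 0.75 × 0.27 = 0.2025; true risk difference -0.0675; loss 10%; 690 per arm; power 80%. From section 4.2: two-sided 5%. The arm-specific loss rates below are assumptions, since the SAP gives none. Except in step 5, drop-outs are assumed to have their arm's risk.

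**1. The plan's sample size.** The two-proportion formula with pooled variance under the null and no continuity correction gives 620.5, so 621 per arm. Then 621 / 0.9 = 690 per arm, 1,380 in total. This reproduces the SAP, and confirms that the sizing treats lost patients as uninformative.

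**2. Equal loss.** Under the rule, observed risk = true risk × (1 - loss), with 690 kept in each denominator.

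- 10% loss: 0.9 × 0.27 = 0.243 and 0.9 × 0.2025 = 0.18225, so the risk difference is -0.06075. Bias is +0.00675 against a standard error of 0.0220. CI coverage is 93.9% and power 78.8%, compared with 80.0% from 621 complete cases per arm. Under the null, type I error is 5.0%.
- 5% loss: risk difference -0.0641, coverage 94.7%, power 81.5%.

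The standard error is not understated. The complete-case value is 0.0240; scaled to the shrunken difference it is 0.9 × 0.0240 = 0.0216, slightly below 0.0220. The fault under equal loss is attenuation, not false precision.

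**3. Unequal loss, no true effect (27% in both arms).** False difference = (control loss - intervention loss) × 0.27.

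| Loss, control / intervention | Overall loss | False difference | Rejection rate |
|---|---|---|---|
| 8% / 12% | 10% | -0.04 × 0.27 = -0.0108 | 7.5% |
| 5% / 15% | 10% | -0.10 × 0.27 = -0.0270 | 21.5% |
| 3% / 7% | 5% | -0.04 × 0.27 = -0.0108 | 7.4% |

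A simulation of 400,000 runs gave 7.49%, 21.52% and 7.47%. The 3% / 7% case is 21 + 48 = 69 of 1,380, exactly 5.0%. That is not larger than 5%, so multiple imputation of the primary outcome would not run.

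**4. Unequal loss, planned effect.** With 12% control and 8% intervention loss: 0.88 × 0.27 = 0.2376 and 0.92 × 0.2025 = 0.1863. The risk difference is -0.0513 and power about 65%.

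**5. Sensitivity to drop-outs' own risk r.** With each arm's overall risk held at 27%, the false difference is (control loss - intervention loss) × r. For a 4-point gap and an assumed r of 10% to 40%, it runs from -0.4 to -1.6 points, with rejection from 5.3% to about 11%.

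**The case against.** On the SAP's own inputs the harm is small: equal 10% loss costs about one point of power and one point of coverage. Equal 5% loss, the most allowed without imputation, leaves power above target. The 10% is a sizing allowance, and section 6.4 expects less. The large errors need assumed imbalances, and both scenarios with 10% overall loss would trigger the imputation. The 3% / 7% case sits exactly at the threshold; one more drop-out would trigger it. The survival re-analysis has no trigger and is close to complete-case, because drop-outs leave the risk set at day one. Imputation replaces one untestable assumption with another, missing at random, and since drop-outs have no outcomes it can draw only on arm and baseline variables.

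Much of this stands. Equal-loss attenuation is modest, the imbalances are hypothetical, and a reader who compares the analyses could see a discrepancy. But these analyses leave the primary estimate and test as they are, and the per-protocol complete-case analysis also removes protocol deviators, so it does not isolate the drop-out rule. Missing at random is also an assumption, but one more credible than zero risk in every drop-out.

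**Conclusion.** The concern holds and should be fixed. The event-free rule governs the primary estimate and rests on an unsupported statement that sits badly with a 27% expected event rate. With balanced loss the cost is small: at most about 0.7 points of risk difference at 10% loss if drop-outs have completers' risk, with type I error intact. With unbalanced loss the primary test is no longer valid: a 4-point gap raises the type I error to about 7.5%, and a 10-point gap to about 22%. These figures depend on the assumed loss rates and on drop-outs' risk. If drop-outs truly had no events the rule would be correct, but the SAP offers nothing to show it.

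A separate inconsistency needs settling. For drop-outs, section 6.4 fixes the censoring time and the count offset at one day, while Table 8 derives both from the last contact date. This affects the survival and count analyses, not the primary binary comparison.

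**What to change.** - In section 6.4, make the multiple imputation of section 6.4.1 the primary handling of a missing 30-day outcome, at any drop-out rate, and delete the 5% trigger.
- Impute from treatment group, the stratification factors, baseline variables and outcomes collected in both arms. Section 6.4.1.1 already limits candidates to baseline variables and outcomes; state explicitly that variables from the intervention-only calls stay out.
- In section 6.3.1.1, state how the Mantel-Haenszel risk difference, its confidence interval and the test are pooled by Rubin's rules.
- Keep the event-free assumption as a sensitivity analysis, and add a delta or tipping-point analysis in which drop-outs' risk varies separately by arm, because imputation assumes missing at random.
- State that drop-out is reported by arm. The planned CONSORT diagram and listings largely provide this.
- Separately, give one rule for drop-outs' censoring time and count offset in section 6.4 and Table 8.

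The cost is SAP wording and minor programming, since 50 imputations are already planned. The confidence interval becomes slightly wider, and a pooled interval and test replace the single-dataset interval and Cochran-Mantel-Haenszel test of section 6.3.1.1.

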6.4.1 Multiple imputations

Multiple imputations will be based on the treatment group, and selected baseline and outcome variables (see next section). Since missing values in these variables are possible, chained equations will be used (e.g. with command `mi impute chained` in Stata). This procedure fills in missing values in multiple variables iteratively based on a sequence of univariate imputation methods with fully conditional specification of prediction equations. Predictive mean matching (`pmm`) will be used for continuous, logistic regression (`logit`) for binary and multinomial regression (`mlogit`) for categorical variables. Survival outcomes will be imputed by adding the log time and the censoring indicator to the imputation model.

Based on such chained equations, a total of 50 multiple imputations will be calculated. If it is not possible to impute all outcomes in one model, a stepwise approach will be considered.

The 50 imputed data sets will be analyzed using Rubin's rules⁹ (e.g. with prefix `mi estimate` in Stata).

6.4.1.1 Selection of variables for multiple imputations

Baseline variable (section 5.5) and outcomes (section 6.1) will be considered for multiple imputations.

Variables with more than 50% missing values will not be used for the imputation model. Binary variables with a frequency of less than 5% in one category will also be omitted. If two binary variables have less than 5% or more than 95% discordant pairs only one of the two will be used (the one with less missings). Levels of ordinal variables with a frequency of less than 5% will be collapsed by adding the entries to the neighbouring category (i.e. next higher or lower level) with the higher frequency (if there are more than one). Categorical variables might generally be recoded if it improves the fit of the imputation model and does not lead to substantial loss of information. Continuous variables will be log-transformed if it improves normality (checked by Shapiro-Wilk tests and QQ plots).

From the remaining variables an imputation model will be constructed based on combined clinical and statistical reasoning. All variables that may provide information about the imputed variable will be included.

6.5 Evaluation of safety parameters

Since the intervention is of very low risk for the patient safety parameters will not be evaluated.

6.6 Statistical software

The statistical analysis will be performed using the statistical software packages Stata¹⁰ and/or R¹¹.

6.7 Quality control

A second statistician will reproduce the analysis of the primary outcome (for both the FAS and the PPS) based on the exported data. The risk difference and the 95% confidence interval should not differ by more than 0.01, the p-value by 0.001. Otherwise, the reason for the difference will be determined and a consensus must be reached.

7 Changes from the protocol

The SAP is consistent with principle features of the statistical methods described in the protocol. The following deviations were made:

Table 10: Changes from protocol

Header	Change	Reason
Blinded analysis	Blinded analysis not implemented	The allocation can immediately be seen from the eCRFs because only patients in the intervention group have follow up phone calls. It would therefore need an extra statistician that carefully prepares the data so that it is not possible to see the allocation. Given the open-label nature of the study and the straightforward analysis this additional effort seems not to be justified.
Secondary outcome "Medication adherence: 4-item Morisky Medication Adherence Scale (MMAS-4)".	Removed	High license fees would incur
Secondary endpoint "Number of planned hospital readmissions" and "Total number of planned days of hospitalizations"	Added	Information about the planned readmissions is of interest but was not considered in the protocol.
Test for the analysis of primary and binary secondary outcome	Stratified Cochran-Mantel-Haenszel test instead of simple chi-squared test	Stratification factor should be considered in the analysis
Subgroup HOSPITAL score	Categories 4 or 5 vs ≥ 6 instead of 5 or 6 vs ≥ 7	Categories correspond to stratification of the randomization
Subgroup clinical site	Added	Used as stratification factor in randomization
Subgroups cancer, living place, living status and health insurance	Added	Of interest, not mentioned in protocol

References

¹ Clinical trial protocol: Transition care intervention targeted to high-risk patients to reduce readmission (TARGET-READ): A randomized controlled trial, Version 1.1, 13.02.2018

² SOP Data preparation and programming, CS_STA_SOP_05, version 02, 15.08.2015

³ SOP Statistical data validation, CS_STA_SOP_02, version 02, 15.08.2015

⁴ Klingenberg, B. 2014. A new and improved confidence interval for the Mantel–Haenszel risk difference. *Statistics in medicine*, 33(17): 2968.

